b. Open-label, multicenter, post-marketing surveillance study, the National Cooperative Growth Study (NCGS), to monitor the safety and efficacy of its rhGH products in children with growth disorders (Genentech, Inc). 1985-2006. N=54,996. Patient years of exposure=192,345.

with 20% (650 patients) estimated to be paediatric patients. In Spain, from 2013-2022, there were approximately 700 patients treated with somatropin, of which 642 received a first dose as a paediatric patient. Similar information from France was unavailable.

Table 3. Estimated Prevalence of Paediatric GHD in each Country, and Estimated Count of Somatropin Patients in each Database

Country	Approx. paediatric population size in selected countries (Millions) ^a	Approx. paediatric GHD prevalent cases in selected countries ^b	Datab ase	Nationa l coverag e (%)	Total approx. number of unique somatropi n patients in database	Total approx. number of unique somatropin paediatric patients in database	Period of coverage of database
France	6.71	1,676	SNDS	99	Unavailable	Unavailable	2009-2019
Spain	9.35	2,337	LPD	3.2	700	642	2013-2022
UK	6.66	1,666	THIN	6	3,375	~650	1995-2020
Sweden	2.20	550	Natio nal registr ies	100	~4,000 per year	~1,700	2008-2019

GHD-Growth hormone disease; Approx-Approximate; LPD-Longitudinal Patient Database; SNDS-The French administrative health care database (Système Nationale des Données de Santé); THIN- The Health Improvement Network.

Sample size calculations were undertaken to estimate the number of patients required to assess each of the primary safety events of interest. All sample size calculations were conducted using PASS software version 20.0.3, with Logrank test.

Sample size calculation to estimate the number of patients required to assess the risk of neoplasms

Sample size calculations were undertaken to estimate the number of patients required to assess the risk of neoplasms. Table 4 presents detectable hazard ratios among somatrogon

PFIZER CONFIDENTIAL

a. Paediatric population (<18 years) approximated to 20% of 2019 population. https://ec.europa.eu/eurostat/documents/2995521/11081093/3-10072020-AP-EN.pdf/d2f799bf-4412-05cc-a357-7b49b93615f1 https://www.populationpyramid.net/europe/2019/

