b. Prevalence of childhood GHD in Europe approximated to be 1/4,000. Orso M, Polistena B, Granato S, et al. Pediatric growth hormone treatment in Italy: a systematic review of epidemiology, quality of life, treatment adherence, and economic impact. PLoS One 2022; 17(2): e0264403. https://doi.org/10.1371/journal.pone.0264403.

treated patients compared with once daily somatropin-treated patients. Assuming a range of 1,305 - 20,000 patients exposed to somatrogon, the minimum hazard ratios (HRs) between treatment groups that could be detected with at least 80% power at the 5% significance level are summarized. Based on the estimates presented in Table 4, assuming 0% annual rate of switching from somatrogon-treated patients to once daily somatropin-treated patients, and 0% annual rate of switching from once daily somatropin-treated patients to somatrogon treated patients, and a neoplasm incidence rate of 0.9/1000 person-years in once daily somatropin-treated paediatric patients (Table 2), sample sizes of 1,305 and 20,000 somatrogon-treated patients would allow for HRs of 3.00 and 1.41, respectively, to be detected between the somatrogon-treated and once daily somatropin-treated groups. Comparative analyses for neoplasms will be performed if there are $\geq 1,305$ patients in the somatrogon-treated group, which would allow for an HR of 3.00 or higher to be detected between somatrogon and once daily somatropin-treated groups. The occurrence of switching will inevitably require a greater sample size and higher thresholds to inform the conduct of comparative analyses.

Table 4. Minimum Detectable Hazard Ratios Among Somatrogon-treated Patients Compared with Once Daily Somatropin-treated Patients with 80% Power, alpha = 0.05, 10-year Study with 5 Years Uniform Accrual, 5% Loss to Follow Up Per Year in Somatrogon-treated group - Neoplasms

Incidence rate per 1,000 person-years of neoplasms in once daily somatropin treated group	Sample size of patients in once daily somatropin treated group (N1)	Sample size in Somatrogon population (N2)	Hazard Ratio
0.9	1,305	1,305	3.00
0.9	2,000	2,000	2.54
0.9	4,000	4,000	2.01
0.9	5,000	5,000	1.89
0.9	10,000	10,000	1.60
0.9	20,000	20,000	1.41

Table 4 assumptions:

- $\alpha = 0.05$
- Power=0.8
- Different somatrogon-treated patient population sizes: n=1,305, 2,000, 4,000, 5,000, 10,000, 20,000
- 1:1 ratio between somatrogon-treated patient population and comparator group of once daily somatropin-treated patients

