9.7. Data analysis

The primary analysis will be descriptive and all eligible patients during the study period will be included, with no upper limit on the sample size. Due to database heterogeneity, analyses will be conducted separately by data source and data will not be pooled.

Baseline demographic and clinical characteristics for each treatment group will be described. For all the safety events of interest and efficacy measurements of interest, descriptive statistics, counts and proportions, crude incidence rates (ie, number of events per person years) and age/sex standardized incidence rates with associated two-sided 95% confidence intervals will be calculated as appropriate.

The summary of event rates will be based on survival analysis of time to first event based on an index date defined for each treatment group with appropriate censoring rules applied for those who do not experience an event by end of follow-up period including those who die, those who are lost to follow-up (eg, via migration out of the country as documented in the data source), or end of study period. Rates will be expressed as events/1,000 person-years of follow-up.

The primary objective of the study is active surveillance (to estimate the incidence rates of neoplasms, and diabetes mellitus type 2, the primary safety events of interest in paediatric patients treated with somatrogon, and paediatric patients treated with once daily somatropin, in the course of routine clinical care). Conducting quantitative, confounding-controlled comparative analyses will depend on having a sufficient sample size. The feasibility of more formal comparative analyses to evaluate safety events of interest that adequately adjust for potential confounders will be assessed in the interim reports, and at study end will be based on statistical power as described below. Since the size of the once daily somatropin-treated comparator group is expected to be a magnitude larger than the somatrogon-treated group,

statistical power will be limited by the uptake of somatrogon (which is difficult to estimate a priori).

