As described in Section 9.5 (Study Size), the comparative analyses by data source will only be performed at the time of the final report if the number of patients in the somatrogon treated group would allow for an HR of 3.00 or higher to be detected with 80% power at the 5% significance level, assuming 0% annual switching between somatrogon and once daily somatropin-treated groups. Specifically, comparative analyses by data source for:

- neoplasms will only be performed at time of the final report if there are $\ge 1,305$ patients in the somatrogon-treated group
- Diabetes mellitus type 2 will only be performed at time of the final report if there are ≥2,344 patients in the somatrogon-treated group.

If comparative analyses can be performed, incidence rates of the primary safety events of interest will be compared between somatrogon-treated patients and the comparator group of daily somatropin-treated patients using multivariable Cox regressions adjusting for potential confounders. The adjusted hazard ratio from the Cox model will be presented along with a 95% confidence interval.

Given the low number of patients anticipated to have IGF-1 laboratory results, height, and weight measurements, and the high potential for missing values/measurements for some clinic visits, no comparative analysis for IGF-1, height, and medication errors will be conducted.

Detailed methodology for summary and statistical analyses of data collected in this study will be documented in a SAP, which will be dated, filed and maintained by the sponsor. The SAP may modify the plans outlined in the protocol; any major modifications of primary endpoint definitions or their analyses would be reflected in a protocol amendment.

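### The 1,305 and 2,344 somatrogon-patient gates meet the stated power criterion only with an equal-sized comparator, which Section 9.7 does not expect, so they can be too high or too low in a given data source

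*Protocol*

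**What the plan says.** Protocol Section 9.5 states: "All sample size calculations were conducted using PASS software version 20.0.3, with Logrank test". Every row of Tables 4 and 5 has equal group sizes, and the assumption lists under both tables include a "1:1 ratio between somatrogon-treated patient population and comparator group of once daily somatropin-treated patients". The rows with HR 3.00 supply the two thresholds.

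Section 9.7 makes these thresholds binding, separately in each data source. The criterion is a somatrogon group whose size "would allow for an HR of 3.00 or higher to be detected with 80% power at the 5% significance level", with no switching assumed. The comparison for "neoplasms will only be performed at time of the final report if there are" at least 1,305 somatrogon patients; for T2DM the figure is 2,344. The abstract (Section 4) and Section 9.5 repeat both numbers.

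The same Section 9.7 says that the "comparator group is expected to be a magnitude larger than the somatrogon-treated group". It includes all eligible patients without an upper limit, does not pool data sources, and plans a multivariable Cox regression. It states no 1:1 matching.

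**The concern.** The thresholds answer how many somatrogon patients are needed with an equal number of comparators. The planned analysis uses every comparator in the source, and the protocol expects many more of them than somatrogon patients. The gate counts somatrogon patients only, so it delivers its own criterion at one allocation ratio, and that is not the ratio the protocol expects.

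At stake is secondary objective c, the hazard ratios for neoplasms and T2DM. The protocol names somatrogon uptake as the limiting factor and each source must pass alone. A gate set too high can withhold a comparison that satisfies the criterion; a gate set too low can admit one that does not.

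**Working it through.** **Inputs (Sections 9.5 and 9.7).** HR 3.00; power 0.80; alpha 0.05 (sidedness not stated; two-sided assumed, and it reproduces the tables); comparator rates 0.9 (neoplasms) and 0.5 (T2DM) per 1,000 person-years; 5 years of uniform accrual, 10 years in total; 5% annual loss in both groups; no switching.

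**Formulas.** Let k be comparators per somatrogon patient, w = 1/(1+k), and p = 3w/(3w + 1 − w).

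- Events: D = [1.960·√(w(1−w)) + 0.842·√(p(1−p))]² / (p − w)²
- Event probability at hazard λ, with loss hazard η = −ln(0.95) = 0.0513 and s = λ + η: P(λ) = (λ/s)·{1 − [exp(−5s) − exp(−10s)]/(5s)}
- Somatrogon patients: n = D / [P(3λ) + k·P(λ)]

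**Reproducing the plan at k = 1.** w = 0.5 and p = 0.75, so D = 28.9.

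- Neoplasms: P(3λ) = 0.01655 and P(λ) = 0.00555, so n = 28.92/0.02210 = 1,308 (stated 1,305).
- T2DM: 0.00923 and 0.00309, so n = 28.92/0.01232 = 2,347 (stated 2,344).

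The 22 rows of Tables 4 and 5 that were tested all agree within 3%, for example 11,691 against 11,688.

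**Changing only the ratio.**

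| Comparator : somatrogon | Events D | Neoplasms n | T2DM n | Gate ÷ n |
|---|---|---|---|---|
| 1:1 | 28.9 | 1,308 | 2,347 | 1.0 |
| 2:1 | 25.1 | 908 | 1,629 | 1.44 |
| 3:1 | 25.8 | 777 | 1,394 | 1.68 |
| 5:1 | 29.8 | 673 | 1,209 | 1.94 |
| 10:1 | 43.1 | 598 | 1,074 | 2.18 |

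At 10:1 for neoplasms, for example, 43.09/(0.01655 + 10 × 0.00555) = 598.

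**Simulated log-rank power at 10:1, HR 3.00.** Neoplasms: 607 patients give 77% to 79%, 650 give 81% to 83%, and 1,305 give 96% to 98%. T2DM: 1,083 patients give 79% to 82%, and 1,150 give 82%. The 10:1 requirement is therefore best given as about 600-650 and 1,070-1,150.

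**Fixing the comparator count instead.** Table 3 lists about 1,700 (Sweden), 650 (UK) and 642 (Spain) paediatric somatropin patients; France is unavailable.

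- 1,700 comparators, neoplasms: about 960 somatrogon patients needed, so 1,305 is about 1.4 times too high.
- 1,700 comparators, T2DM: about 6,100 needed; 2,344 gives about 70% power (69% to 70% across formula and simulation).
- 650 comparators, neoplasms: 1,305 gives about 54% to 56% power. However large the somatrogon group, the formula levels off near 65%.
- 650 comparators, T2DM: it levels off near 29%.

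**T2DM rate.** At 0.1 per 1,000 person-years, 10:1 requires about 5,360 somatrogon patients. With a 10:1 comparator, 2,344 keeps 80% power down to about 0.23 per 1,000.

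**The case against.** The 1:1 ratio is disclosed and the tables are correct for it, so this is no arithmetic error. That stands: the fault is a mismatch between the sizing assumption and the planned analysis.

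A reader might infer that both gates are simply twice what is needed and that adequately powered comparisons will be suppressed. The documents do not support that as a general statement. A magnitude is not a fixed ratio, and at 2:1 the factor is only 1.4. The 10:1 figures need about 6,000 to 10,700 comparators in one source, far above any count in Table 3, so they are realistic mainly for France, whose count is unknown. Table 3 holds historical counts rather than projections, but they show that the gate can also err on the low side.

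A high gate also leaves slack. Section 9.5 says that switching raises the thresholds, and the Cox model adjusts for confounders while the calculation does not. If covariates explained 20% to 30% of the variance in treatment (an assumption), 598 would become about 750 to 850 (598/0.8 to 598/0.7). At 600 patients and 10:1, only about 10 somatrogon neoplasms are expected under HR 3.00 and about 3 under no effect. This is a good reason not to adopt 600 and 1,070 as new gates. It does not rescue 1,305 and 2,344, because Section 9.7 defines them explicitly at zero switching and 80% power.

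The size of the effect depends on the approximation. The Schoenfeld formula falls only about 7% between 1:1 and 10:1 (1,177 to 1,092 for neoplasms), while the Freedman formula falls about threefold (1,420 to about 460). Neither reproduces the stated figures, and the simulations support the formula used above.

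Finally, the primary analysis is descriptive, feasibility is reviewed in the interim reports, and the SAP may modify the plan. This limits the severity.

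**Conclusion.** The inconsistency is real. The two gates implement the stated criterion only at 1:1. For comparators 2 to 10 times larger they are about 1.4 to 2.2 times too high. For small comparators, a gate on somatrogon patients alone can be too low: about 70% power for T2DM at 2,344 against 1,700 comparators, and 80% unattainable for either outcome against about 650.

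These figures rest on two-sided alpha, zero switching, no covariate adjustment and the protocol's own rates. For T2DM they hold only at 0.5 per 1,000 person-years, near the top of the Table 2 range of 0.016 to 0.52. The documents do not establish that the gates are uniformly twice too high.

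Only secondary objective c is affected; the primary incidence rates are not. This should be fixed, but it does not undermine the study.

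**What to change.** In Sections 4, 9.5 and 9.7, replace the fixed somatrogon counts with one rule applied in each data source: run the comparison if the minimum detectable HR at 80% power and the 5% level is at most 3.00, given the actual numbers or person-years in both groups and the assumed comparator rate. State that rate for each outcome. Add 3:1, 5:1 and 10:1 rows to Tables 4 and 5 as illustration, not as new fixed gates.

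The cost is a re-run of the sample size software and some rewording; no extra data are needed. The downside is that sources with few comparators may face a higher threshold than now, or may not qualify at all.

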9.6. Data management

All data for this study will be collected through the routine data collection practices of databases in the 4 participating countries. Investigators in each country will either independently generate the data needed for the study by linking the national databases or receive study specific data generated by the owner of the databases (ie, responsible authorities).

Overall, the study will follow the European Network of Centres for Pharmacoepidemiology and Pharmacovigilance (ENCePP) and the International Council for Harmonisation (ICH) guidelines for data management. The process for data management may vary by country however, the investigators will check the data for consistency in terms of range of values, units of measurement, and relevance of clinical information. Additionally, frequency tables of variables of interest will be generated to check for plausibility and consistency.

Details regarding utilizing data from the 4 countries and other aspects of data management are below:

France

Based on the data extraction criteria provided by Certara France, the Caisse nationale de l'Assurance Maladie (CNAM) statisticians will search for patients within the SNDS and will develop the relevant targeting algorithm. After validation of this algorithm with Certara France, the CNAM will extract the data required for this study. As this is an extraction from the SNDS claims database, no specific data are collected from patients or doctors.

The extracted data will then be made available to the Certara France project team in a dedicated project area on the SNDS portal (subject to the favourable opinion of the relevant committees). Authorized Certara France users will be able to access data extracted from the portal. Certara France is committed to strictly respecting the benchmark determining the criteria of confidentiality, expertise and independence for research laboratories and design offices provided for by the decree of 17 July 2017.

The data will be kept for the number of years authorized for the conduct of the study and the publication of the results, then they will be permanently deleted.

The data will be received from SNDS in text format according to the selection criteria of the study. SAS® software (SAS Institute Inc., Cary, North Carolina, United States) or R will be used to process the data, including its management and analysis, manage the analytic

datasets, and conduct data analysis. This study will follow the relevant chapters of the European Network of Centres for Pharmacoepidemiology and Pharmacovigilance (ENCePP) and the International Conference on Harmonisation (ICH) guidelines for data management. In addition, the data will be checked for consistency in terms of range of values, units of measurement, and relevance of clinical information (eg, a pregnancy diagnosis for a male patient).

Spain

In Spain, data will be extracted from EMR as text files and stored on secure IQVIA servers in a dedicated data folder accessible only to trained IQVIA personnel involved in the study. Datasets will be extracted for analysis as specified in the Data Management Plan and SAP, following standard IQVIA procedures.

The LPD databases collect medical information from proprietary practice management software used by the physician during patients' office visits for recording their daily patient interactions in EMRs. A panel of physicians using this software volunteers to make available anonymized, patient-level information from their practices for clinical research purposes. Data are entered during usual patient care and submitted to the co-ordinating centers, cleaned and de-identified. This data collection allows retrospective analysis of a patient's written prescriptions and care history within a single panel practice.

The data are hosted on servers located in data centers belonging to IQVIA, which ensures a high level of data security and confidentiality. All European data are collected and processed in full compliance with General Data Protection Regulation (GDPR) and local privacy regulation requirements.

Data analysis and results generation will strictly follow the approved SAP. If for any reason any statistical method needs to be carried out in different way than described in the SAP, amendment to the SAP with required documentation and new approval is essential. Data will be analysed using Statistical Analysis System (SAS) version 9.4 (or upper) or R, or other similar statistical software.

Sweden

In Sweden, national healthcare registers cover almost the entire Swedish population. Identification of health outcomes and treatment groups for this study will use nationwide Swedish healthcare registers, as described in Section 9.4. The team will ensure correctness of the raw data (although not monitor) before data management starts. Records from different registries will be merged by unique personal identifier and pseudonymized before delivery of the datasets to the research team. More specifically, the information to be used from the various registers will be linked by the National Board of Health and Welfare (NBHW). The NBHW is a register holder and responsible for the information in the national health registers. The NBHW will link information from the registers through the personal identification numbers (PINs). The PIN is given to each citizen of Sweden at birth or

immigration. The datasets constructed by NBHW will be delivered to Karolinska Institutet Center of Pharmacoepidemiology, without the PINs. The PIN has been substituted by a serial number, allowing to identify an individual, without revealing her or his identity (pseudonymization). Patient-level data are kept on secure servers, and will not be made available to the Sponsor. Delivery of coded format data in SAS files from the National Board of Health and Welfare and Statistics, Sweden is possible and will be exported, managed, and analysed using SAS or R .

UK

THIN® database is regulated by an Advisory Committee to ensure that it continues to be used in a way that maximises its research value in the best interests of the public whilst protecting the rights of its data subjects.

THIN® database is compliant with GDPR and approved by the National Health Service (NHS) Research Ethics Committee. The database is anonymised at source (not personal data) and patients can opt out at any point of records being collected.

9.7. Data analysis

The primary analysis will be descriptive and all eligible patients during the study period will be included, with no upper limit on the sample size. Due to database heterogeneity, analyses will be conducted separately by data source and data will not be pooled.

Baseline demographic and clinical characteristics for each treatment group will be described. For all the safety events of interest and efficacy measurements of interest, descriptive statistics, counts and proportions, crude incidence rates (ie, number of events per person years) and age/sex standardized incidence rates with associated two-sided 95% confidence intervals will be calculated as appropriate.

The summary of event rates will be based on survival analysis of time to first event based on an index date defined for each treatment group with appropriate censoring rules applied for those who do not experience an event by end of follow-up period including those who die, those who are lost to follow-up (eg, via migration out of the country as documented in the data source), or end of study period. Rates will be expressed as events/1,000 person-years of follow-up.

The primary objective of the study is active surveillance (to estimate the incidence rates of neoplasms, and diabetes mellitus type 2, the primary safety events of interest in paediatric patients treated with somatrogon, and paediatric patients treated with once daily somatropin, in the course of routine clinical care). Conducting quantitative, confounding-controlled comparative analyses will depend on having a sufficient sample size. The feasibility of more formal comparative analyses to evaluate safety events of interest that adequately adjust for potential confounders will be assessed in the interim reports, and at study end will be based on statistical power as described below. Since the size of the once daily somatropin-treated comparator group is expected to be a magnitude larger than the somatrogon-treated group,

statistical power will be limited by the uptake of somatrogon (which is difficult to estimate a priori).

As described in Section 9.5 (Study Size), the comparative analyses by data source will only be performed at the time of the final report if the number of patients in the somatrogon treated group would allow for an HR of 3.00 or higher to be detected with 80% power at the 5% significance level, assuming 0% annual switching between somatrogon and once daily somatropin-treated groups. Specifically, comparative analyses by data source for:

- neoplasms will only be performed at time of the final report if there are $\ge 1,305$ patients in the somatrogon-treated group
- Diabetes mellitus type 2 will only be performed at time of the final report if there are ≥2,344 patients in the somatrogon-treated group.

If comparative analyses can be performed, incidence rates of the primary safety events of interest will be compared between somatrogon-treated patients and the comparator group of daily somatropin-treated patients using multivariable Cox regressions adjusting for potential confounders. The adjusted hazard ratio from the Cox model will be presented along with a 95% confidence interval.

Given the low number of patients anticipated to have IGF-1 laboratory results, height, and weight measurements, and the high potential for missing values/measurements for some clinic visits, no comparative analysis for IGF-1, height, and medication errors will be conducted.

Detailed methodology for summary and statistical analyses of data collected in this study will be documented in a SAP, which will be dated, filed and maintained by the sponsor. The SAP may modify the plans outlined in the protocol; any major modifications of primary endpoint definitions or their analyses would be reflected in a protocol amendment.

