9.4. Data sources

This study plans to utilize administrative healthcare databases in France, electronic secondary data collected in the Spain LPD database, the national population-based electronic healthcare registers in Sweden, and electronic primary healthcare records database in the UK. These secondary data sources are selected based on the availability of the expected required data elements and projected number of patients with somatrogon exposure post-approval within the data source country. The inclusion of their data in all reports will reflect data availability at the time of data base lock for each report. The proposed data sources are briefly described below:

- France-The French administrative health care claims database ('Système National des Données de Santé', SNDS) covers approximately 99% of the total 67 million population. In addition to demographic characteristics, SNDS contains outpatient data including drugs dispensation with number of units, laboratory tests performed (tests results are not captured), and registration status in the long-term disease database for chronic conditions identified with ICD-10 codes. In SNDS, somatrogon (and somatropin) will be mainly self-administered by the patient in the outpatient sector (including a first administration supervised by a physician). In the case where treatment is administered and invoiced during a hospitalization, data will be available only if the treatment is registered in the 'list en sus' or 'retrocession list'. The outpatient data are linked to hospitalisation data (national hospital discharge database, PMSI) through a unique personal identification number (Scailteux and Droitcourt, 2019). The PMSI captures information relating to inpatient or ambulatory care admissions to a public or private hospital in France, including discharge diagnoses, procedures and drugs administered during hospitalization and invoiced in addition to the diagnosis-related group (DRG). All diagnoses are coded according to ICD-10. Height and weight measurements are not available in this claims database. The contents of SNDS include but are not limited to:
 - Sociodemographics: age (through date of birth (MMYY)), sex, lowest income level (based upon whether patient is a recipient of basic universal health coverage), and deprivation index.

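### The comparative analyses are gated source by source at thresholds computed for 1:1 allocation, so on the protocol's own counts Spain and the UK would contribute nothing to the hazard-ratio objective (2c)

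*Protocol*

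**What the plan says.** Section 9.7 sets the structure: "Due to database heterogeneity, analyses will be conducted separately by data source and data will not be pooled". The abstract says the same.

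Section 9.7 also says that "the comparative analyses by data source will only be performed at the time of the final report if the number of patients" of somatrogon users is large enough to detect HR 3.00 with 80% power. It fixes this at 1,305 for neoplasms and 2,344 for type 2 diabetes. These figures come from Tables 4 and 5 in section 9.5, which give hazard ratios that could be "detected with at least 80% power at the 5% significance level". Both tables assume equal group sizes. Section 9.7 itself expects the somatropin group to be a magnitude larger than the somatrogon group.

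Section 9.5 gives these paediatric somatropin counts:
- Spain (LPD, 2013–2022): about 700 patients, "of which 642 received a first dose as a paediatric patient".
- UK (THIN, 1995–2020): about 3,375 patients, "with 20% (650 patients) estimated to be paediatric patients".
- Sweden: about 1,700 in 2019.
- France: no treated count. Table 3 offers only 1,676 prevalent GHD cases.

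Secondary objective 2c is to estimate hazard ratios for neoplasms and type 2 diabetes.

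**The concern.** A gate on each source, with no provision for bringing the source results together, discards comparative information from every source that is too small alone. If two of the four sources cannot reach the gate on the protocol's own counts, objective 2c rests on the other two. One of those has no treated count, and the other would need a large share of its patients on the new product.

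The thresholds add to the problem. They are presented as the size at which HR 3.00 becomes detectable, but that holds only for equal groups. With a much larger comparator, fewer somatrogon patients meet the same criterion, so the rule can block analyses that satisfy its own stated standard. A ten-year post-authorisation safety study could then end with fewer comparative estimates than its data support.

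**Working it through.** **1. Reproducing the thresholds.** Section 9.5 says: "All sample size calculations were conducted using PASS software version 20.0.3, with Logrank test". Inputs from Tables 4 and 5: alpha 0.05 (two-sided reproduces the figures), 80% power, comparator rate λ of 0.9 or 0.5 per 1,000 person-years, 5 years' uniform accrual, 10 years in total, 5% annual loss in both groups (η = −ln 0.95), no switching.

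Let θ(t) be the ratio of somatrogon to somatropin patients at risk and d(t) the expected events at time t. Then, summing over time:
- S = Σ d·[HR·θ/(1+HR·θ) − θ/(1+θ)]
- V0 = Σ d·θ/(1+θ)²
- V1 = Σ d·HR·θ/(1+HR·θ)²
- Power = Φ[(S − 1.96·√V0)/√V1]

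For 1,305 per group, λ = 0.9/1,000 and HR 3.00: S = 7.225, V0 = 7.213, V1 = 5.428. So (7.225 − 1.96 × 2.686)/2.330 = 0.842, and power is 80.0%. Solving for n gives about 1,305 and 2,343 per group, against 1,305 and 2,344 stated. Ten other rows of Tables 4 and 5 agree within 3%.

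**2. Spain and the UK at 100% uptake.**
- Spain: 642/1,305 = 49%; 642/2,344 = 27%.
- UK: 650/1,305 = 50%; 650/2,344 = 28%. The 650 accrued over 26 years, so ten years would give about 650 × 10/26 = 250, or 250 × 3.3/2.3 ≈ 359 if the active panel grows as section 9.4 foresees.
- Section 9.4 also mentions about 2,300 under-18s with GHD in THIN. Scaled the same way, 2,300 × 10/26 ≈ 885, still below 1,305.

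**3. Sweden.** 1,305/1,700 = 77% and 2,344/1,700 = 138%, but 1,700 is a single-year count. Adding new starters over 5 years with an assumed mean treatment duration D gives 1,700 + 5 × 1,700/D, that is 3,825 (D = 4) to 2,550 (D = 10) ever-users. The uptake needed is then 34–51% for neoplasms and 61–92% for diabetes.

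**4. France.** Table 3's footnote reads: "Paediatric population (<18 years) approximated to 20% of 2019 population". Section 9.4 says SNDS "covers approximately 99% of the total 67 million population". Twenty per cent of 67 million is 13.4 million, and 13.4 million/4,000 = 3,350 GHD cases. Table 3 has 6.71 million (10%) and 1,676. The UK entry of 6.66 million would be 20% of only 33.3 million. The protocol gives no UK total, but section 9.4 puts 2.3 million active patients at about 4% of the population, which implies 57.5 million. The UK row therefore appears to be halved as well. Sweden's row is consistent with the footnote (2.20/10.2 = 22%).

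**5. The gate at the expected allocation.** The same formula at 10:1 needs about 600 (neoplasms) and 1,076 (diabetes at 0.5/1,000) somatrogon patients. Conversely, a source meeting the 1,305 gate at 10:1 would hold 1,305 × 11 = 14,355 paediatric GH users.

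**6. Combining the sources (illustration).** Uptake is assumed, since the protocol gives none. The base is 642 + 650 + 1,700 plus France at 1,676 or 3,350, that is 4,668 or 6,342. Uptake of 20% implies 4:1 and 10% implies 9:1. HR is 3.00.

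| Uptake | Combined n | Needed, neoplasms | Power | Needed, diabetes | Power |
|---|---|---|---|---|---|
| 20% (4:1) | 934 | 713 | 88% | 1,279 | 69% |
| 20% (4:1) | 1,268 | 713 | 95% | 1,279 | 80% (79.7) |
| 10% (9:1) | 467 | 608 | 72% | 1,091 | 53% |
| 10% (9:1) | 634 | 608 | 81% | 1,091 | 63% |

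Under these assumptions the largest single source is France at 0.20 × 3,350 = 670, so none passes 1,305. The combined 1,268 would also fail the unadjusted 1,305 despite 95% power, so combining without restating the gate does not solve the problem. With THIN at 250 and France at 1,676, neoplasm power is 86% at 20% uptake and 69% at 10%.

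**The case against.** Four points on the other side carry weight.

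- **A reader might infer that no source can qualify and that 2c will go unanswered.** The documents do not support this. France has no treated count, and GHD prevalence is no ceiling on treated patients: Sweden has 550 prevalent cases but about 1,700 users, a ratio of 3.1. If that ratio is assumed for France at 3,350 cases, there would be about 10,350 treated children, and 1,305 would need about 13% uptake (2,344 about 23%). Correcting Table 3 thus makes France more likely to pass.
- **A reader might infer that Table 1 promises 2c in all four databases.** Its title concerns which databases hold the relevant data. It says nothing about adequate numbers.
- **A reader might infer that combining results is forbidden.** Section 9.7 rules out pooling data and does not mention meta-analysis of source estimates. It also lets the SAP modify the plan. That leaves the fix open, but the by-source gate and its two thresholds are fixed in the protocol itself.
- **The comparison is openly conditional.** Sections 9.7 and 9.9 say that it depends on sample size and uptake, and feasibility is to be assessed in the interim reports. This limits the severity. However, the protocol never says that two of its four sources fall short on its own counts.

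Database heterogeneity is a sound reason not to merge patient records. It does not count against combining aggregate estimates with heterogeneity reported.

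**Conclusion.** The concern holds for Spain and the UK and for the way the thresholds are set. On the protocol's counts those two sources reach at most about half of 1,305 and 28% of 2,344 at full uptake, so they would add nothing to objective 2c. This rests on historical somatropin counts continuing to describe the two databases. For Sweden and France the outcome depends on unknown uptake: 1,305 is possible and 2,344 is harder.

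The thresholds are about 2.2 times what the stated criterion requires at 10:1 (1,305/600 and 2,344/1,076).

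The combined-power figures assume the stated uptake, a common hazard ratio, no switching and no loss of information from confounder adjustment, so they are upper-end illustrations. The diabetes figures also depend on 0.5 per 1,000 person-years. At 0.1, which the protocol also considers, 10:1 allocation needs about 5,356 somatrogon patients, far above any combined number here.

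The defect touches a conditional secondary objective. The primary descriptive analysis still runs.

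**What to change.** - Keep the source-specific analyses and pre-specify a two-stage combination. Each source fits the same model and supplies its log hazard ratio and standard error, or its event and person-year counts for a source-stratified exact or Poisson model that keeps sources with zero events. Report between-source heterogeneity.
- Apply the HR 3.00 / 80% power criterion to the combined set, recalculated at the observed or expected allocation ratio. Do not carry over the 1:1 figures of 1,305 and 2,344.
- State in sections 9.5 and 9.7 that Spain and the UK are not expected to qualify alone.
- Correct the France and UK rows of Table 3 to the stated 20% (France about 3,350 GHD cases instead of 1,676), or change the footnote.

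The cost is protocol and SAP wording plus a small analysis of aggregate output, with no sharing of patient-level data. The downside is that heterogeneity between sources may widen the combined interval, and at low uptake the combined set may still fall short, particularly for diabetes.
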